Study Title: Dosing of ketorolac

NCT: NCT03464461

Date: 5/12/2021

Dosing of ketorolac

[name] Pharm.D., [name] PhD., [name] MD

05/12/2021 v6

1. Objective and Specific Aims

The non-steroidal anti-inflammatory drugs (NSAID's) are very commonly used to treat pain in Emergency Departments. In January of 2018 more than 1100 doses of the injectable NSAID ketorolac were given in the University of Missouri Emergency Department. The correct dosing of ketorolac is unclear.

Our study is designed to clarify the optimal dose of ketorolac.

2. Background and Significance

Background

Optimal pain management in the Emergency Department remains problematic[1]. NSAID are a particularly useful class of drugs in Emergency Departments because of their effectiveness and safety[2]. The parenteral form of ketorolac has become particularly popular for treatment of acute pain in Emergency Departments, demonstrated by the total of more than 1100 doses given in the University of Missouri Emergency Department in January of 2018 (internal audit).

Recently the optimal dosing of ketorolac has been questioned[3]. This study showed equal efficacy among three doses of intravenous ketorolac: the standard 30mg dose, 15mg, and 10mg. These investigators recommended a change in practice to adopt the 10mg dose as standard.

Significance

The correct dosing of analgesics and ketorolac is actually a complicated and poorly understood issue. Ketorolac, as with other NSAID's, has multiple properties that may influence its analgesic properties; it has anti-inflammatory properties similar to other NSAID, is an analgesic, and is an inhibitor of prostaglandin synthesis[2]. Also it has significant placebo effect in some circumstances. In a study of acute headaches in an Emergency Department three intramuscular injections were compared: meperidine 50mg with 25mg promethazine, ketorolac 60mg, and saline[4]. The three treatments were found to be effective and equivalent. The authors conclude that the placebo effect was so profound that analgesic effects could not be evaluated. There is also evidence that ketorolac and other NSAID's have different efficacy as a function of

the type of pain[2]; that is, that pain which is inflammation mediated may be more very responsive.

3. Objectives and Purpose

This study is designed to determine the optimal dose of ketorolac in four groups of patients that would be expected to have different mechanisms of response to NSAID's.

4. Research Design and Methods

Methods

Patients presenting to the Emergency Department with pain will be screened for inclusion into one of four groups:

1. Headache: Non-traumatic headache of less than four days duration.
2. Trauma: Patients with acute mild to moderate musculo-skeletal injury (no trauma activation) or pain of less than four days duration.
3. Colic/Abdominal pain: Patients with mild to moderate abdominal or flank pain of less than four days duration.
4. Viral syndrome: Patients with less than four days of generalized systemic complaints suggestive of an acute viral syndrome.

A pregnancy test will be administered to females of childbearing potential before administration of the study drug. Patients will be randomized to receive either 30mg of ketorolac, 10mg of ketorolac, or saline as a slow intravenous infusion over 10 minutes via a pump. Thirty minutes or later their pain score will be re-evaluated, they will be assessed for any negative effects of the treatment, additional pain medications will be offered if indicated, and the patient's involvement in the study will be concluded.

Data collected:

1. Patient demographics
 - a. Age
 - b. Sex
 - c. Complaint
2. Pain scores
3. Side effects noted by patient or staff

5. Subjects

Subjects will be eligible for recruitment when they present to the Emergency Department with a chief complaint consistent with the four study groups. Inclusion criteria will be:

1. Age \geq 18y/o
2. Not pregnant or lactating (negative urinary pregnancy test)
3. No contraindication to ketorolac

Exclusion criteria

1. Age $<$ 18y/o
2. Pregnancy or lactation
3. Contraindication to ketorolac

If the subjects are eligible for inclusion they will be offered inclusion in the study by one of the Emergency Department faculty. If they refuse participation they will be treated in a standard fashion.

6. Treatment of subjects

There will be no long term follow up of patients for data. Subjects who have incomplete data will have their data discarded and removed from enrollment.

7. Statistics

End point: the primary hypothesis is that ketorolac has different effects depending on the dose and the condition. We will compare pain scores at 30 minutes or after for each of the doses and the groups.

Sample size: We plan to enroll 170 patients in each group. This is based on a change in pain scale of 2.5 with a standard deviation of 2.5, and α of 0.05 and power of 0.80[5].

An interim analysis will be performed when half of the patients are enrolled in each group. The study will be terminated if there is significant difference in the groups at this point. [name] is providing statistical support for the project.

8. Direct access to source data/documents

Access to source data and documents will be provided by the investigators for any auditing or monitoring or reviews by the IRB/IEC, or regulatory inspections.

9. Ethics

This trial proposes to study the proper dosing of ketorolac in several different conditions and attempts to clarify the placebo effect in this setting. Standard care will not be withheld at any time during this protocol. The intervention may offer significant benefit for the patients being studied. An interim analysis is planned with termination of the study if this is the case.

10. Data handling and recordkeeping

Initial data collection will include identification of the patient by name and medical recorded number. This data will be kept in a locked cabinet in the Emergency Medicine Department. Data will be extracted from these records and recorded in a computer data base and identified only by subject number. No patient identifiers will be entered in to the computer database.

11. Investigators

[name]: [name] is Pharm.D. with extensive training in the clinical use of the medications involved in this study and a [history of working in the emergency department](#).

[name]: [name] is Pharm.D. with extensive training in the clinical use of the medications involved in this study whose clinical duties are in the Emergency Department.

[name]: [name] is an Associate Professor of Emergency Medicine. He is attending physician in the Emergency Department and routinely manages patients with headache.

[name]: [name] is Research Assistant Professor in the Department of Emergency medicine and has extensive training in research.

12. Financing and insurance

Patients will have regular charges for Emergency Department visit but will not be charged for ketorolac/placebo or its administration. Charges for any treatment will be per usual. There will be no payments to the subjects.

13. References

1. Patrick, P.A., et al., *Timely pain management in the emergency department*. Journal of Emergency Medicine, 2015. **48**(3): p. 267-73.
2. Catapano, M.S., *The analgesic efficacy of ketorolac for acute pain*. Journal of Emergency Medicine, 1996. **14**(1): p. 67-75.

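### With no minimum pre-dose pain score and a severity limit on only some conditions, effect sizes are understated and the dose-by-condition comparison is partly confounded with starting severity

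*Combined protocol and SAP*

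**What the plan says.** The opening of Section 4 asks for pain but gives no score: "Patients presenting to the Emergency Department with pain will be screened for inclusion into one of four groups". The four definitions that follow treat severity in two ways.

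- Headache has no limit: "Headache: Non-traumatic headache of less than four days duration".
- Trauma has a limit, attached to the injury: "Patients with acute mild to moderate musculo-skeletal injury (no trauma activation) or pain of less than four days duration". Whether the limit also governs the pain in that sentence is unclear.
- Abdominal or flank pain has a limit on the pain itself: "Colic/Abdominal pain: Patients with mild to moderate abdominal or flank pain of less than four days duration".
- Viral syndrome has no limit, and its own definition does not mention pain: "Patients with less than four days of generalized systemic complaints suggestive of an acute viral syndrome".

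Section 5 adds only age, pregnancy or lactation, and contraindication to ketorolac. Recruitment otherwise rests on the presenting complaint: "Subjects will be eligible for recruitment when they present to the Emergency Department with a chief complaint consistent with the four study groups".

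Section 7 makes a difference in effect by dose and by condition the primary hypothesis, and compares pain scores taken at 30 minutes or later. On sample size it says: "This is based on a change in pain scale of 2.5 with a standard deviation of 2.5". Section 4 has the score re-evaluated after treatment, so a pre-dose score is evidently taken. No section says how it will be used, and the pain scale is not named.

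**The concern.** A pain score cannot fall below zero. A patient who starts low has little room to improve, and less room to improve further than a patient given saline. Enrolling such patients shrinks the observed difference between ketorolac and saline even when the drug works as well as planned.

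The uneven limits carry this into the primary question. If one condition may not enrol severe pain and another may, the capped condition can show a smaller effect only because its patients started lower. Section 3 expects the four conditions to differ in mechanism of response, so a floor effect could be read as a mechanism. Randomisation balances the arms within a condition. It does nothing to make starting severity alike between conditions.

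Section 2 makes the issue more pressing. It describes a headache trial whose authors thought the placebo response too large for analgesic effects to be judged. The larger the fall on saline, the less room is left for the drug.

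**Working it through.** **Inputs from the documents.** Difference 2.5, SD 2.5, alpha 0.05, power 0.80 and 170 per group (Section 7); three arms and four conditions (Section 4).

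**Assumptions, because the documents are silent.** A 0-10 scale; a two-sided test; 1:1:1 allocation; group meaning condition, so 170/3 = 56.7 per arm; the 2.5 read as the drug-saline difference; whole-number starting scores equally likely within each range; mean fall 1.5 on saline and 4.0 on drug.

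**1. The plan's own figure.** n per arm = 2 × (1.96 + 0.84)² × (2.5/2.5)² = 15.7, so 16 per arm, or 48 for a three-arm condition. The stated 170 does not follow from the stated inputs. Nothing below depends on its derivation, only on about 57 per arm being enrolled.

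**2. The strict floor.** From a start below 2.5, a fall of 2.5 is impossible. Room for a 2.5-point advantage over saline needs a start of at least the saline fall plus 2.5. Below that the difference is compressed, not necessarily abolished.

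**3. Size of the compression.** Post-dose score = start − 1.5 (saline) or start − 4.0 (drug) + N(0, 2.5), cut at 0 and 10. SE = √[(SD²saline + SD²drug)/56.7]. Power = Φ(difference/SE − 1.96).

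| Starting scores | Observed difference (true 2.5) | SD saline | SD drug | SE | Power |
|---|---|---|---|---|---|
| 1-3 | 0.98 | 1.70 | 0.87 | 0.254 | 97% |
| 1-6 | 1.48 | 2.38 | 1.59 | 0.380 | 97% |
| 1-10 | 1.80 | 3.21 | 2.68 | 0.555 | 90% |
| 4-6 | 1.98 | 2.41 | 1.86 | 0.404 | >99% |
| 4-10 | 2.15 | 2.88 | 2.71 | 0.526 | 98% |
| 7-10 | 2.28 | 2.41 | 2.57 | 0.468 | >99% |

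The floor shrinks the SD along with the difference, which is why power holds even for starts of 1-3.

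**4. False interaction.** The true benefit is 2.5 in both conditions, and the drug-saline differences are compared without adjustment for the pre-dose score.

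- 1-6 against 1-10: gap 1.80 − 1.48 = 0.32; SE = √(0.380² + 0.555²) = 0.673; ratio 0.47. A two-sided 5% test rejects about 8% of the time.
- 1-6 against 7-10: gap 2.28 − 1.48 = 0.80; SE = √(0.380² + 0.468²) = 0.603; ratio 1.33. The test rejects about 27% of the time.

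**5. Sensitivity to the saline response.** The same model was run with other saline falls, keeping the true benefit at 2.5.

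- Fall of 0: gaps 0.07 (SE 0.744) and 0.18 (SE 0.627), with rejection about 5% and 6%.
- Fall of 3: gaps 0.50 (SE 0.570) and 1.27 (SE 0.553), with rejection about 14% and 63%. Pairwise power is then 88% for starts 1-10 (1.52/0.488) and 85% for starts 1-3 (0.51/0.171).

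**The case against.** The case against has real force on several points.

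**Power.** A reader might infer that low scorers add noise and push the trial towards finding no difference. The table does not bear this out at the planned size. A cruder check agrees. If half the patients are mild with a true difference of 0.5 to 1.0, the mean difference is 0.5 × 2.5 + 0.5 × 0.5 = 1.5, up to 0.5 × 2.5 + 0.5 × 1.0 = 1.75. Power at 57 per arm with SD 2.5 is then 89% to 96%.

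**Viral patients without pain.** A reader might infer that a viral patient scoring 0 is eligible. The opening of Section 4 restricts screening to patients with pain, and the groups named in Section 5 are drawn from those patients. The viral definition needs clearer wording; it does not cancel that requirement.

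**Four different limits.** The text does not limit severity differently in each condition. Two conditions carry mild-to-moderate wording and two carry none.

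**Size of the confounding.** The contrast the text itself sets up, capped against unrestricted, gives only 8% against a nominal 5%. The 27% needs an uncapped condition whose patients nearly all start at 7-10, which no definition states. Larger figures need further assumptions. If relief is the same 31% to 50% of the starting score everywhere, and mean starts are 4 in one condition and 7-8 in another, the false-positive rate is 29% to 85%. None of those inputs is in the documents.

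**Limits of a common minimum.** Starts of 4-6 and 7-10 still give 1.98 and 2.28, a gap of 0.30. A shared minimum therefore needs adjustment for the pre-dose score alongside it.

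Open enrolment of emergency patients may also be deliberate. That would explain the missing minimum, but not a limit on some conditions and not others.

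**Conclusion.** The point stands as a weakness in interpretation. It does not invalidate the randomised comparison of doses within a condition. Under the stated assumptions a true 2.5-point benefit would be reported as about 1.5 to 2.3 points, depending on where patients start. The primary dose-by-condition comparison would be partly confounded with starting severity, modestly (about 8%) on the ranges the text implies and materially (about 27%) if uncapped conditions draw mostly severe pain. Pairwise power is about 90% or more at the central assumption and about 85% at its lowest in the range tried.

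The sizes rest on the 0-10 scale, the saline fall, the spread of starting scores and 1:1:1 allocation, none of which the documents give. The direction, with the capped condition showing the smaller difference, held for saline falls of 0, 1.5 and 3, though at 0 the gap is negligible. The documents do not support a claim that the trial would miss an effect, or that any particular cut-off is right.

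**What to change.** - **Section 5:** name the pain scale. Require a score recorded before randomisation, at or above one pre-specified minimum, with the same permitted score range in all four conditions. The sponsor should choose and justify the cut-off, for example as the lowest score that leaves room for the planned 2.5 points beyond the expected saline fall.
- **Section 4:** state in the viral definition that pain is required, in line with the opening sentence. Reconcile the severity wording across the four groups. Whether severe abdominal pain may be enrolled is a clinical matter for the sponsor.
- **Section 7:** compare doses and conditions with adjustment for the pre-dose score and a baseline-by-dose term. This handles differences in starting severity that a shared range leaves behind. It cannot recover relief that the floor hides, so it complements the entry criterion and does not replace it.

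The cost is a text amendment with no new procedure, since a pre-dose score is evidently already taken. Recruitment would be somewhat slower, and the results would not apply to very mild pain.

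### Section 6 discards subjects with incomplete data, with no exception after randomisation, so the pain comparison and interim decision rest on completers and side effects of removed subjects leave the study dataset

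*Combined protocol and SAP*

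**What the plan says.** The rule is one sentence in Section 6 (Treatment of subjects): "Subjects who have incomplete data will have their data discarded and removed from enrollment". It has two parts: the data go, and the subject no longer counts as enrolled.

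Four other places bear on it.

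- **Section 4 (Research Design and Methods).** Subjects are randomised to ketorolac 30 mg, ketorolac 10 mg or saline, infused over 10 minutes. Pain is scored again at 30 minutes or later, and at that point "they will be assessed for any negative effects of the treatment". The data list has three items: demographics, pain scores, and "Side effects noted by patient or staff".
- **Section 7 (Statistics), end point.** "We will compare pain scores at 30 minutes or after for each of the doses and the groups". It names no analysis population, missing-data method or sensitivity analysis.
- **Section 7, interim.** "An interim analysis will be performed when half of the patients are enrolled in each group". Then: "The study will be terminated if there is significant difference in the groups at this point".
- **Sections 8 and 10.** Source documents are open to audit and IRB review. Of the initial identified records, Section 10 says: "This data will be kept in a locked cabinet in the Emergency Medicine Department".

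**The concern.** Randomisation makes the arms comparable as allocated. Dropping subjects for something that happens after allocation can undo this if those dropped differ in outcome from those kept and the difference does not balance across arms. Here the rule tells the team to drop them, and by un-enrolling them it also takes them out of the count a reader would use to see how many were lost from each arm. The plan does not forbid reporting losses by arm, but it does not require it.

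Take a subject who is infused, has a side effect noted by staff, and leaves or declines before the second pain score. Under Section 6 that subject drops out of the pain comparison, the side-effect data and the enrolment count that triggers the interim look. The side-effect loss does not depend on any imbalance between arms, and it matters in a trial whose purpose is to choose a dose.

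Because incomplete is undefined, a literal reading would also remove a subject with a valid post-dose score and a missing demographic item.

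**Working it through.** **Does the rule reach randomised subjects?** The second pain score comes at least 30 minutes after a randomised infusion (Section 4). A subject without it has incomplete data on any reading. Section 6 does not restrict itself to screening or pre-dose failures, and Sections 7, 8 and 10 do not bring removed subjects back into the analysis. So it does.

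**Inputs from the plan.** 170 per group, difference 2.5, SD 2.5, α 0.05 (Section 7); three arms and four condition groups (Section 4). The plan gives no loss rate, so there is no figure of its own on this point to reproduce. The 170 does not follow from the stated inputs: 2 × (1.960 + 0.842)² × (2.5/2.5)² = 15.7, or 16 per arm. That is a separate matter, and nothing below depends on it.

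**Assumptions.** Allocation 1:1:1; 170 is the total per condition, so 170/3 ≈ 57 per arm; two-sided tests; SD of retained scores 2.5; loss rates and gaps as shown.

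**Bias formula.** Let p be the fraction discarded in an arm and gap the mean score of discarded minus retained subjects. Then

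retained mean = all-randomised mean − p × gap,

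so the bias in arm A minus arm B = (p_B × gap_B) − (p_A × gap_A).

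This is 0 if the gaps are 0, or if loss and gap are both equal across arms. Equal loss alone is not enough: at 5% v 5% with gaps of +2.5 and −2.5, the absolute bias is 0.05 × 2.5 + 0.05 × 2.5 = 0.25.

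**Absolute bias with a common gap in both arms**

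| Loss | Gap 1 | Gap 2.5 |
|---|---|---|
| 10% v 5% | 0.05 × 1 = 0.05 | 0.05 × 2.5 = 0.125 |
| 20% v 5% | 0.15 × 1 = 0.15 | 0.15 × 2.5 = 0.375 |

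Against the planned difference: 0.05/2.5 = 2% and 0.375/2.5 = 15%.

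**Effect on one pairwise test within a condition.** SE = 2.5 × √(2/56.67) = 0.470.

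- No true difference (t-test): type I error is 0.051 at bias 0.05, 0.058 at 0.125 and 0.124 at 0.375.
- True difference 2.5 with the largest bias against it: 2.5 − 0.375 = 2.125, and power is 0.994.
- Interim, 85/3 ≈ 28 per arm, tested at 0.05 by assumption because no boundary is given: type I error is 0.054 at 0.125 and 0.086 at 0.375.

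**Counts, only if removed subjects are replaced and allocation is 1:1:1.** With 4 × 170 = 680 retained:

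- 5% loss in every arm: 680/0.95 = 716 randomised, 36 removed.
- 20% on saline and 5% in each ketorolac arm, averaging 10%: 680/0.90 = 756 randomised, 76 removed.
- The interim at 85 counted subjects per condition would come after 85/0.95 = 89 to 85/0.90 = 94 randomised.

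If removed subjects are not replaced, the sample shrinks instead, to 170 × 0.95 = 161.5 or 170 × 0.90 = 153 per condition.

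**The case against.** The strongest reply is that little may be lost. There is a single assessment within the same emergency visit, and involvement then ends. Nothing in the documents supports 20% loss in one arm against 5% in another, and every effect above is zero if no data are incomplete. This stands. The bias figures illustrate and do not estimate, and the case for the change does not rest on them.

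A reader might infer that the rule biases the trial, or does so in a known direction. The documents do not show this, since they give neither loss rates nor reasons. A reader might also push the illustration further by assuming that the worst scorers are lost from one arm and the best from another. Nothing in the documents supports that pattern. Cutting off a tail would also shrink the retained SD below 2.5, so power and type I error computed with the SD held at 2.5 would not fit the scenario. No such figures are relied on here.

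On side effects, a reader might infer that the events vanish altogether. That goes too far. Identified initial records are kept (Section 10) and are open to review (Section 8), and the documents do not say whether discarding reaches them. Nor does Section 7 plan an analysis of side-effect rates. What the text supports is that these events leave the study dataset.

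Replacement of removed subjects is an inference from their un-enrolment and is not stated.

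None of this supplies an exception after randomisation, an all-randomised set or another missing-data rule.

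**Conclusion.** The point holds. Section 6 is an explicit instruction, and following it makes the pain comparison and the interim stopping decision depend on completers. It also takes side effects of removed infused subjects out of the study dataset and leaves no required account of losses by arm. These consequences follow from the text without any assumed loss rate.

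The size and direction of any bias are unknown. Under the assumptions listed it runs from 0 to 0.375 points with a common gap. At the upper end the exposure is a false difference (type I error about 0.12) more than a missed one (power about 0.99). The weight of the point lies in the missing all-randomised accounting and the missing side-effect data, and the sentence should be changed. Some passages of the document were not available for this review, and nothing in the visible text points to an exception there.

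**What to change.** Replace the Section 6 sentence with:

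> All randomised subjects remain enrolled and are counted, including for the half-enrolment interim trigger, and losses are reported by arm with reasons where known. Efficacy is analysed by assigned arm using every recorded post-dose pain score; a missing demographic item does not exclude a subject. A simple sensitivity analysis shows how far missing post-dose scores could change the result. Side effects are reported for everyone who received any infusion.

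Multiple imputation is an option for the missing scores, not a requirement. With one post-dose assessment and few covariates it may add little to an available-case analysis with simple bounds.

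Cost: two short items added to the Section 4 data list (infusion status and reason for loss) and a little extra analysis. No extra patients are needed.

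### Section 7 hypothesises effects that vary by dose and condition but names no dose-by-condition test, states no analysis role for the pre-dose score, and does not tie the interim look to a named dose comparison or an alpha split

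*Combined protocol and SAP*

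**What the plan says.** Section 7 (Statistics) gives the hypothesis: "the primary hypothesis is that ketorolac has different effects depending on the dose and the condition". Section 3 (Objectives and Purpose) supplies the rationale, describing "four groups of patients that would be expected to have different mechanisms of response".

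The only analysis statement, also in Section 7, is "We will compare pain scores at 30 minutes or after for each of the doses and the groups". No test, model, interaction term, contrast, covariate or multiplicity rule is named there or elsewhere.

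Section 4 (Research Design and Methods) randomises patients to three arms: 30 mg, 10 mg or saline. It says "Thirty minutes or later their pain score will be re-evaluated" and lists pain scores among the data collected. A pre-dose score is therefore implied, but no section says how it enters the analysis. Entry severity differs by condition: one group is "Headache: Non-traumatic headache of less than four days duration", with no severity limit, while another is "Patients with mild to moderate abdominal or flank pain of less than four days duration".

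The sample size is 170 in each group, with alpha 0.05 and power 0.80: "This is based on a change in pain scale of 2.5 with a standard deviation of 2.5". On the interim look, Section 7 says "An interim analysis will be performed when half of the patients are enrolled in each group", and the study stops if the groups differ significantly. Section 9 (Ethics) links that stop to the intervention proving beneficial to the patients.

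**The concern.** A claim that the effect depends on the condition is a claim about how dose contrasts differ across conditions. The planned sentence can be carried out in two ways, and neither tests that claim.

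- **Dose comparisons within each condition.** These are valid, but a significant result in one condition and a non-significant one in another does not show that the effects differ.
- **Post-dose comparisons between conditions.** Patients are not randomised to conditions, so a gap can simply reflect how much pain each group started with.

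With no test named, the test of the primary hypothesis can be chosen after the data are seen. Two lesser costs follow. Precision is lost if a score that the trial appears to collect anyway is not used. An interim look with no named comparison and no alpha allocation also raises the false-positive rate.

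**Working it through.** **Inputs.** From the documents: 3 arms, 4 conditions, 170 per group, SD 2.5, alpha 0.05, power 0.80, one interim look at half enrolment. Assumed: group means condition, equal allocation (170/3 = 56.7 per arm), two-sided tests, and 2.5 as the SD of the post-dose score. The documents give no baseline scores or pre/post correlation, so ranges are shown.

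**The plan's own figure.** For a two-arm comparison with difference 2.5 and SD 2.5, n per arm = 2 x (1.960 + 0.842)^2 x (2.5/2.5)^2 = 15.7, so 16 (17 by the t-test). That is 48 to 51 per three-arm condition, not 170. This mismatch is a separate matter; 170 is taken as given below.

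**Precision within a condition.** The standard error of a dose contrast is 2.5 x sqrt(2/56.7) = 0.470. The difference detectable with 80% power (t-test) is 1.33 points. Adjusting for the pre-dose score multiplies this by sqrt(1 - rho^2):

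| rho | Factor | Detectable difference |
|---|---|---|
| none | 1 | 1.33 |
| 0.3 | 0.954 | 1.27 |
| 0.5 | 0.866 | 1.15 |
| 0.6 | 0.800 | 1.06 |

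If 2.5 is instead the SD of change (equal pre and post variances assumed), the post-dose SD is 2.5/sqrt(2(1 - rho)). The unadjusted figures at rho 0.3/0.5/0.6 become 1.12/1.33/1.48 and the adjusted ones 1.07/1.15/1.19.

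**Separate tests do not show a difference between conditions.** Suppose all four conditions share one true effect. With power p in each, the chance of a mix of significant and non-significant results is 1 - p^4 - (1 - p)^4.

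- Effect 1.0 point: p = 0.560, mixed 86%.
- Effect 1.33 points: p = 0.802, mixed 59%.
- Effect 2.5 points: p = 0.9995, mixed 0.2%.

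**Between-condition post-dose comparisons.** With 170 per condition the standard error is 2.5 x sqrt(2/170) = 0.271. With no difference in drug effect, a post-dose gap of 0.25, 0.5 or 1.0 point is significant 15%, 45% or 96% of the time. These gaps are hypothetical.

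**Interaction power.** Let one condition's effect (both active arms against saline) differ from the other three by d. The noncentrality of the 6-df F test (error df 668) is 56.7 x (d/2.5)^2 x (2/3) x (3/4), divided by 1 - rho^2 when the pre-dose score is in the model.

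| d | rho | Noncentrality | Power at 0.05 | Power at 0.047 |
|---|---|---|---|---|
| 1.0 | 0 | 4.53 | 30% | 29% |
| 1.3 | 0 | 7.66 | 51% | 49% |
| 1.0 | 0.5 | 6.04 | 40% | 39% |
| 1.3 | 0.5 | 10.22 | 65% | 64% |

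**Two looks.** The test statistic was simulated under no effect at half and full information (4 million draws per row):

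| Test used at both looks | 0.05 and 0.05 | 0.005 then 0.047 |
|---|---|---|
| One dose contrast (1 df) | 8.3% | 4.9% |
| Overall dose test (2 df) | 8.4% | 4.9% |
| Interaction (6 df) | 8.5% | 4.9% |

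**The case against.** The strongest reply is that the trial may want only dose comparisons within each condition. Section 3 seeks the best dose in four groups, Section 9 speaks of proper dosing in several conditions, and the analysis sentence can be read that way. Those comparisons are randomised and answer that aim. This reading is natural, and it narrows the point. It does not remove it, because the hypothesis in Section 7 still says the effect depends on the condition, and separate tests cannot establish that.

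Much of the size is also conditional. The starting-pain gaps and correlations are assumed, and mixed verdicts almost vanish at the planned 2.5 points. That limits the harm if effects are as large as planned; it does not supply the missing test.

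A reader might infer three stronger things that the documents do not support:

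- **That a gap in starting pain between conditions could stop the study at half enrolment.** Section 7's rule speaks loosely of groups, but Section 9 ties stopping to benefit from the intervention, which points to a treatment comparison.
- **That the pre-dose score is not collected or has no role at all.** Section 4 implies it is taken, and the sample-size sentence refers to a change. Only its role in the analysis is unstated.
- **That leaving out baseline biases the dose comparisons.** Within a condition it costs precision only.

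**Conclusion.** The point holds as a gap in specification. The primary hypothesis has no named test, the pre-dose score has no stated analysis role, and the interim rule names no dose comparison and shares no alpha. The randomised within-condition dose comparisons remain valid.

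The precision cost is modest: a detectable difference of 1.33 points where 1.06 to 1.27 may be attainable. It rests on equal allocation, an SD of 2.5 for the post-dose score and correlations of 0.3 to 0.6, and the figures change if 2.5 is the SD of change. The false-positive rate of 8.3% to 8.5% needs only two looks at 0.05 with the interim at half information. Mixed verdicts matter only if effects are well below plan. This should be fixed, and it is a cheap improvement.

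**What to change.** Replace the analysis sentence in Section 7 with wording such as:

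> The post-dose pain score will be analysed in one linear model with pre-dose pain score, condition, dose and dose x condition. Whether the dose effect differs by condition will be tested by the dose x condition term (6-df F test). The 12 within-condition dose contrasts will be reported with confidence intervals whatever the interaction result. No conclusion about drug effect will be drawn from post-dose differences between conditions.

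Also:

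- State in Section 4 that the pre-dose score is recorded before the infusion.
- Reconcile the interim rule in Section 7 with Section 9 by naming the randomised dose comparison that it uses. Split alpha for any test used at both looks; 0.005 then 0.047 keeps each such test at or below 5%, though not several tests jointly.
- Say whether the 2.5 change is within patients or between arms, and which quantity its SD describes.
- State the interaction power.

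**Cost.** Wording only; no extra patients. The downsides to declare are interaction power of about 30-51% for a 1.0-1.3 point difference (40-65% with correlation 0.5) and a slightly smaller final alpha, which lowers that power by about one percentage point. Multiplicity adjustment over the 12 contrasts is optional and is a trade-off. Bonferroni would raise the within-condition detectable difference from 1.33 to 1.77 points (1.54 with correlation 0.5), while power at the planned 2.5 points would remain 99%.
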